## 3.0 Eligibility Criteria

## 3.1 Inclusion Criteria

- Healthy volunteers
- Able to understand and complete the Informed Consent
- Both males and females
- Age between 18-65 years
- All ethnic backgrounds

## 3.2 Exclusion Criteria

- Patients or limited health conditions
- Under the age of 18 years or above the age of 65 years
- Smoking tobacco product
- Prisoners
- Cannot consent for themselves

• Pregnant individuals

## 4.0 Study Design

## 5.0 Enrollment/Randomization

Potential subjects will be identified from IU School of Medicine staff members. Each subject will use all four devices.

## 6.0 Study Procedures

First the subjects will go through a questionnaire session about their medical history by a designated study team member. The questionnaire data will be placed in RedCap using a subject ID that cannot be linked back to the subject. Then the subject will be consented. Subject will be enrolled. Then the non-invasive data collecting procedure will start on the following equipment:

Spatial Frequency Domain Imaging (SFDI): During consenting period, the Modulim equipment will be calibrated and setup ready for scanning. Subject's volar aspect of the thumb along with the palm surface

will be ready to target the optical camera head. Actual scanning takes less than 60 seconds. The images will be processed offline. During processing 3-5 different regions of interest (ROI) will be taken to measure the oxygen parameters such as tissue oxygen saturation (StO2), oxy-hemoglobin (HbO2), deoxy-hemoglobin (HbR), superficial hemoglobin (HbT1, sub-surface hemoglobin (HbT2). The model used is a Clarifi Modulum

**Transcutaneous oxygen monitoring (TCOM)**: Transcutaneous oxygen monitoring (TCOM or TcpO2) is a noninvasive, clinically-approved method to obtain skin oxygen levels. The method is quantitative, and measures oxygen delivery to the skin from underlying tissue. Before positioning the electrode, an adhesive fixation ring will be placed on the dry skin on the volar aspect of the thumb and an electrolyte as a contact liquid will be filled half and the probe is aligned into it by rotating clock-wise to fasten it. Recording will be started and waited for the oxygen level to stabilize and a fixed value will be recorded. The model used is a Perimed PeriFlux 5000. The probe will be heated to about 45°C. Although this device has other options, only the measurement of  $O_2$  will be performed using this device.

**Apple Watch Oxygen Sensor**: Smart watch blood oxygen sensors also measure blood oxygen level in the tissue. Apple Watch Series 6 introduced this new feature for monitoring blood oxygen level using light emitting diodes (LEDs) at the back of apple watches. A low blood oxygen level can be indicative of a serious health issue that needs immediate attention. The apple watch is equipped with green, red, and infrared LEDs that shine light onto the blood vessels in the wrist, with photodiodes measuring the amount of light reflected back. Apple's algorithms use this information to calculate the color of the blood, which is an indication of how much oxygen is in the blood. Bright red blood is well oxygenated, while darker blood has less oxygen. This can measure blood oxygen levels between 70 and 100 percent. Most healthy people have blood oxygen levels that range from 95 to 100 percent. The apple watch sensor will be positioned on the user's preferred wrist.

Pulse Oximeter for Oxygen Monitoring: The pulse oximeter enables transcutaneous monitoring of the oxygen saturation of hemoglobin in arterial blood ( $StO_2$ ). Pulse oximetry is so widely prevalent in medical care that it is often regarded as a fifth vital sign[3]. It is important to understand how the technology functions as well as its limitations. To recognize the settings in which pulse oximeter readings of oxygen saturation (SpO2), an understanding of two basic principles of pulse oximetry is required: (i) how oxyhemoglobin (HbO2) is distinguished from deoxyhemoglobin (HbR) and (ii) how the SpO2 is calculated only from the arterial compartment of blood. Pulse oximetry is based on the principle that HbO2 and HbR differentially absorb red and near-infrared (IR) light. It is fortuitous that HbO2 and HbR have significant differences in absorption at red and near-IR light because these two wavelengths penetrate tissues well whereas blue, green, yellow, and far-IR light are significantly absorbed by non-vascular tissues and water [3]. HbO2 absorbs greater amounts of IR light and lower amounts of red light than does HbR; this is consistent with experience – well-oxygenated blood with its higher concentrations of  $HbO_2$  appears bright red to the eye because it scatters more red light than does HbR. On the other hand, HHR absorb more red light and appears less red. Exploiting this difference in light absorption properties between HbO2 and HbR, pulse oximeters emit two wavelengths of light, red at 660 nm and near-IR at 940 nm from a pair of small light-emitting diodes located in one arm of the finger probe. The light that is transmitted through the finger is then detected by a photodiode on the opposite arm of the probe. In this study, volar aspect of thumb and index finder of the subject will be used to measure SpO2. The model is Innovo iP 900AP.

Sequence of the events during the study visit:

- 1) Consenting and enrolling the subjects
- 2) Medical questionnaire
- 3) Fitzpatrick's skin type assessment

- 4) Non-invasive imaging and data collection of the thumb and index fingers with the above devices in the following order:
  - a) Baseline imaging and data collection
  - b) Occlusion of the blood flow using pressure cuff at 200mmHg for 2 minutes and then collect the data during occlusion. There is a minimal risk of pain on the arm inflation of the pressure cuff up to 200mmHg. Please see literature (1) where they have used 240mmHg.
  - c) Releasing the cuff and collecting the data during the hyperemic phase (post-deflation of the cuff).

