## 9.0 Statistical Considerations

Five sets of data will be collected from each of the devices and statistical mean and standard error of deviation from the mean will calculated.

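### The only TCOM reading rule, waiting for a stable value, does not fit the 2-minute occlusion or the untimed hyperaemic phase, so the moment a TcpO2 value represents is undefined

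*Protocol*

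**What the plan says.** Protocol section 6.0 (Study Procedures) describes TCOM in one paragraph: fix the ring, fill it with electrolyte, fasten the probe, and then "Recording will be started and waited for the oxygen level to stabilize and a fixed value will be recorded". No other TCOM reading rule appears in either document.

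The sequence of events later in section 6.0 calls for "Non-invasive imaging and data collection of the thumb and index fingers with the above devices in the following order", and lists three phases:

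- step 4a, baseline;
- step 4b, "Occlusion of the blood flow using pressure cuff at 200mmHg for 2 minutes and then collect the data during occlusion";
- step 4c, "Releasing the cuff and collecting the data during the hyperemic phase (post-deflation of the cuff".

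TCOM is one of those devices, and section 5.0 confirms that "Each subject will use all four devices". The hyperaemic phase has no stated start, length or sampling time. For SFDI, section 6.0 says "Actual scanning takes less than 60 seconds".

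Section 10.0 (Statistical Data Management) says that TCOM, pulse oximeter and watch data are written down with pen and paper and then entered electronically. It mentions neither a saved TCOM trace nor time stamps.

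Under its first Q2, the SAP lists four time points for the five SFDI parameters: baseline, occlusion, reactive hyperaemia and recovery. Recovery is therefore distinct from hyperaemia in the study's own scheme.

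**The concern.** A wait-for-stability rule suits a steady state, which baseline should be. The other two phases exist to make oxygen change. If the operator waits for a plateau during occlusion, it may not arrive before the cuff is released. If the operator waits after release, the value may belong to what the SAP calls recovery. If the operator gives up waiting, the value is pre-plateau, or there is none.

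The protocol does not say which of these should happen, so practice could differ between subjects and between operators. TcpO2 could also be read at a different moment from the other devices in the same nominal phase.

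At stake is the comparison of devices, which is the subject of the secondary objective (section 1.2) and the secondary outcome (section 2.2). A difference in timing could pass for a difference between devices. It would be hard to correct afterwards, because a single handwritten value without a time cannot be re-aligned.

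**Working it through.** The plan states no figure on this point, so there is none to reproduce. The check sets the rules side by side and then illustrates when the stability rule could fit the occlusion window.

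**1. The rules by phase**

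| Phase | Time available | TCOM rule | Does the rule fix the moment of reading? |
|---|---|---|---|
| Baseline | not limited | wait for stability | Yes in principle, though no stability criterion is given |
| Occlusion | 2 minutes = 120 s | none specific to the phase | Only if a plateau is reached in time |
| Hyperaemia | not stated | none specific to the phase | No |

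**2. Occlusion: illustration**

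Assumption: TcpO2 approaches its new level as a first-order response with time constant τ. The documents give no τ, so a range is shown.

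- Share of the change reached at time t: f(t) = 1 − exp(−t/τ), with t = 120 s.
- Time to 95% of the change: −τ × ln(0.05) = 2.996 × τ.

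| τ (s) | f(120 s) | Still to come at 120 s | Time to 95% (s) |
|---|---|---|---|
| 30 | 1 − exp(−4) = 0.982 | 2% | 90 |
| 60 | 1 − exp(−2) = 0.865 | 14% | 180 |
| 120 | 1 − exp(−1) = 0.632 | 37% | 359 |

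The largest τ for which a given share is reached within 120 s is 120 / −ln(1 − share):

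- 90%: 120 / 2.303 = 52 s
- 95%: 120 / 2.996 = 40 s
- 99%: 120 / 4.605 = 26 s

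The rule therefore fits inside the occlusion if settling is fast and overruns it if settling is slow. The documents do not say which applies.

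**3. Occlusion: the repeated sets**

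Section 9.0 says "Five sets of data will be collected from each of the devices" without saying whether that is per phase or per visit. If it is per phase and all five fall inside the 2 minutes, each set has 120 / 5 = 24 s per device. With only 24 s per set, waiting afresh for a plateau before each one would be harder still.

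**4. Hyperaemia**

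No duration is given, so nothing can be calculated. The rule and the phase can only be compared in words: one asks for a settled value, the other for a value during the response to release.

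**5. Which analyses are touched**

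- The SAP's regression models by sex and by skin type use StO2, HbO2, HbR, HbT1 and HbT2. All are SFDI outputs, so these models are not affected.
- TCOM appears in the SAP only in the title and the abbreviation list. Its correlation question does not name TCOM, and no device-agreement analysis is specified.
- The effect therefore falls on whatever device comparison is made under sections 1.2 and 2.2 of the protocol.

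**The case against.** The strongest reply is that the stability sentence closes the description of probe placement, is in the singular and names no phase. It can be read as a single settling step before baseline, with the probe left in place and read again later. This reading is possible and is not refuted here. But it leaves no TCOM rule at all for occlusion and hyperaemia, so the moment of reading stays undefined.

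A second reply is that steps 4b and 4c require collection during each phase, and nothing tells staff to read TCOM after a phase has ended. This stands. A reader might infer that the rule necessarily gives values from the wrong phase, or that a stable value after release cannot be hyperaemic. The documents support neither. The first depends on a settling time they do not give. The second depends on a time course of hyperaemia they do not describe, so a brief hyperaemic plateau is not excluded. A pre-plateau or missing value is as possible as a late one.

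Third, "for 2 minutes and then collect the data during occlusion" can mean that collection starts after 2 minutes with the cuff still inflated. The 2 minutes would then be settling time and 120 s would not be an upper limit. This also stands as a reading. Waiting for stability would then give the occlusion a variable, unstated length, so the timing remains unresolved.

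Finally, false disagreement between devices is not a certain result. The plan specifies no agreement analysis, and the secondary objective compares the other modalities with pulse oximetry, not TCOM with SFDI in particular.

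**Conclusion.** The point holds as a mismatch between a single reading rule and two phases it does not suit. On any of the readings above, the moment that a TcpO2 value represents during occlusion or hyperaemia is either undefined or set by a plateau that may not come in time. Late, pre-plateau and missing values are risks, not certainties.

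The size depends on the assumed first-order response. A reading at 120 s would miss about 2%, 14% or 37% of the change for time constants of 30, 60 or 120 s, and the rule fits the window at the 95% level only up to about 40 s. These figures also take the 2 minutes as the whole occlusion. No size can be given for hyperaemia.

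The consequence is a possible distortion of the device comparison. It does not reach the SAP's sex and skin-type models. The gap should be closed before data collection, because the planned paper record would not allow readings to be re-timed later.

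**What to change.** Reconcile the TCOM paragraph of section 6.0 with steps 4b and 4c:

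- State that the wait-for-stability rule applies to baseline only, and say what counts as stable.
- For occlusion and hyperaemia, record TcpO2 at pre-specified, time-stamped points common to all subjects. Examples are the last value before cuff release and, after release, either the value at a fixed time or the peak with its time.
- State whether the 2 minutes contain or precede data collection.
- Time-stamp the readings of the other devices, including the SFDI image, so that values can be matched within a phase.
- Say how a reading is recorded when no plateau has been reached.

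The cost is modest: protocol wording and slightly more recording work. Section 10.0 mentions only pen and paper, so either the TCOM trace must be saved or the times written down with the values.

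The change standardises timing but does not make the response faster. The end-of-occlusion value may still be short of a plateau and should be reported as such.

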## **Background & Rationale**

Pulse oximeters are commonly utilized medical devices used to measure blood oxygen saturation (SpO2)[2]. These devices (such as the INNOVO Fingertip Pulse Oximeter) are either stand-alone or integrated into physiologic monitoring systems, using 2 wavelengths of lights to determine SpO2. With recent advances in technology, Spatial Frequency Domain Imaging (SFDI) using range of light wavelengths from red to near infrared (NIR) such as in Clarifi(R) (Modulated Imaging, Inc., Irvine CA), smartphones such as Apple Watch (Apple Inc., Cupertino, CA), transcutaneous oximetry TCOM (Perimed Inc., Las Vegas, NV) now have pulse oximetry capabilities. Since it is possible that most patients could utilize this technology, we sought to assess the accuracy, reliability and usability of these oximeters and compare outcomes. In this study, a cohort of 20 healthy volunteers above the age of 18 including males and females of different skin colors will be assessed at the same site and data will be compared. We aim to provide a set of data that will support the clinical and scientific community and identify more than one reliable skin oxygen measurement modalities. The Innovo pulse oximeter device will be used for all subjects.

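### Three of the four devices share the thumb, and no device order or reading time is planned, so same-site device comparisons during occlusion and hyperaemia mix device with elapsed time

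*Protocol*

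**What the plan says.** The protocol is a within-subject device comparison. Section 5.0 states: "Each subject will use all four devices". The Background plans "a cohort of 20 healthy volunteers above the age of 18" and says they "will be assessed at the same site and data will be compared". The secondary objective (1.2) is to compare the other modalities with pulse oximetry.

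Section 6.0 places the devices as follows:

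- **SFDI:** a camera views the "Subject's volar aspect of the thumb along with the palm surface". On duration: "Actual scanning takes less than 60 seconds".
- **TCOM:** "an adhesive fixation ring will be placed on the dry skin on the volar aspect of the thumb". A heated probe is then fastened into the ring, and one value is taken once the reading has stabilised. No stabilisation time is given.
- **Pulse oximeter:** thumb and index finger.
- **Watch:** the wrist the subject prefers.

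Step 4 of the visit sequence says that data are collected "with the above devices in the following order". The items listed under it are phases: (a) baseline, (b) cuff occlusion, (c) release and hyperaemia. For occlusion the cuff is applied "for 2 minutes and then collect the data during occlusion". No time window is given for the hyperaemic phase.

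Neither document states a device order, a rotation, simultaneous reading, time stamps, separate hands or a separate cuff cycle per device. The SAP has four labelled time points and no term for device order or for time within a phase.

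**The concern.** The cuff is used to make tissue oxygenation change. During and after occlusion, a reading depends both on the device and on how many seconds have passed since the cuff went up or came down. When devices need the same piece of skin, they cannot be read at the same instant. Unless order and timing are controlled or recorded, a lag between readings can look like a device difference, or like a different response to the cuff, even where two devices track the tissue equally well.

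What is at stake is the secondary objective in the phases after baseline. A lag that runs the same way in every subject does not average out, so a larger sample would not remove it. The analysis cannot repair it either, because the reading times are not among the planned data.

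**Working it through.** The documents give no sample size, power or precision figure for the device comparison, so there is nothing of theirs to reproduce. Four checks follow.

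**1. Can the readings be simultaneous?** From section 6.0, the TCOM ring and probe cover volar thumb skin that the SFDI camera has to see, and an oximeter on the thumb competes for the same digit. SFDI, TCOM and a thumb oximeter must therefore be read in turn if the site is to be the same. The watch, and the oximeter when on the index finger, are on other sites and could be read alongside a thumb device.

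**2. Is reading time short relative to the phase?** The occlusion is 2 minutes = 120 s, and one SFDI scan takes up to 60 s.
- One scan: 60/120 = 0.5, up to half of the occlusion.
- Section 9.0 asks for five sets of data from each device. If that means five scans per phase (an assumption), SFDI alone could take 5 × 60 = 300 s, longer than the occlusion.
- TCOM adds an unstated stabilisation time.

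**3. Can device be separated from reading position?** Take one phase with 20 subjects and four readings each (80 rows), treated as serial. The model is reading = subject + device + position, with 20 + 3 + 3 = 26 columns.
- One order common to all subjects: each device column equals a position column, so three are redundant. Rank = 26 − 3 = 23 of 26, and no device contrast can be separated from position.
- Four balanced orders, 5 subjects each: rank 26 of 26. The standard error of a device contrast, in units of the within-subject SD, is √(2/20) = 0.316. This equals that of the unadjusted paired contrast, so balancing costs no precision.
- SFDI and oximeter only, 10 subjects in each order: the device contrast is the average of the two order-specific mean differences. Its variance is ¼ × (2/10 + 2/10) = 2/20, so the standard error is again 0.316. A drift of rate × lag enters with opposite signs in the two halves: (10 × drift − 10 × drift)/20 = 0. This requires the drift to be additive, the lag to be the same in both orders, and no carry-over.

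**4. How large could the effect be?** Apparent difference = lag × rate of change. Both inputs are assumptions; the documents give neither.

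| Lag | 2 points/min | 5 points/min | 10 points/min |
|---|---|---|---|
| 0.5 min | 1 | 2.5 | 5 |
| 1 min | 2 | 5 | 10 |
| 2 min | 4 | 10 | 20 |

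The lag is capped at 2 minutes because that is the stated length of the occlusion.

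**The case against.** Several counter-arguments have force.

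- **No fixed device order is written.** A reader might infer from the order in which section 6.0 describes the devices (SFDI, TCOM, watch, oximeter) that the oximeter is always read last, so that device and time are fully confounded. The documents do not support that. The section describes the devices one by one, and step 4 orders phases only. Complete aliasing is conditional on staff using one order throughout.
- **Not all readings are serial.** The watch and the index-finger oximeter can be read alongside a thumb device. This stands, but such a pairing compares different sites, and nothing in the plan asks for it.
- **A larger figure is tempting.** Four readings one minute apart would give a 3-minute lag and, at the same rates, 3 × 2 = 6 to 3 × 10 = 30 points. That lag is longer than the 2-minute occlusion and ignores parallel reading.
- **The devices do not share a scale.** SFDI gives tissue saturation and haemoglobin parameters, TCOM a skin oxygen level, and the oximeter arterial saturation. A figure in points can illustrate only the saturation readings. Nor is the SAP's example interval for the sex difference in StO2 a useful yardstick: it is a between-subject contrast at time 1, not a device contrast.
- **The planned models are untouched.** The SAP's sex and skin-type regressions use five SFDI parameters from the same scan, so device order does not enter them. The SAP specifies no between-device model.
- **Full rotation may not be workable.** TCOM needs a ring, contact liquid, a heated probe and stabilisation on the same thumb. Refitting it around a 2-minute occlusion is doubtful, and local heating could carry over to later readings.

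These points limit the reach and size of the concern. They do not supply an order, a clock time or a time term, and the secondary objective is not confined to baseline.

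**Conclusion.** The point holds for same-site device comparisons in the occlusion and hyperaemic phases. Order and timing are unspecified and unrecorded there, so device is mixed with elapsed time. One common order would make the two inseparable; an unrecorded, varying order would leave uncontrolled noise and possibly bias.

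The size is unknown. The illustrative 1 to 20 points rests wholly on the assumed lags and rates, and applies to saturation readings only.

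The baseline comparison is not affected, since the cuff is not then changing the tissue, and neither are the SAP's SFDI-only sex and skin-type results. This is a change the sponsor should make to protect the secondary objective; it does not invalidate the study.

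**What to change.** 1. Counterbalance the devices that can be moved quickly: for example, SFDI first in 10 subjects and oximeter first in the other 10, keeping each subject's order in every phase.
2. Keep TCOM at one fixed, stated point in the sequence, or on a separate site. Do not try to rotate it.
3. Read the wrist watch and the index-finger oximeter at the same moment as a thumb device.
4. Write the clock time of every reading, SFDI scans included, on the paper form described in section 10.0.
5. Specify the device comparison in the SAP with elapsed time or reading position as a term, and report any remaining TCOM timing confounding as a limitation.
6. Reconcile the passages on timing. Step 4b leaves unclear whether readings fall within or after the 2 minutes, and the SAP has a recovery time point that steps 4a to 4c lack.

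The cost is a pre-printed order list, one extra column on the form and an operator who follows a per-subject order. No extra subjects or visits are needed. Counterbalancing reduces the effect of non-simultaneous reading but does not make readings simultaneous.

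The SAP already quotes a sex split and fitted estimates. If data collection is complete, items 1 to 3 come too late for these subjects. What remains is to use any reading times that can be recovered and to report the limitation.
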